3.2 Proposed Study Investigation with Correlative Studies

MRD negativity after induction (with/without consolidative ASCT) is an increasingly important outcome for patients with multiple myeloma. The management of low burden disease (VGPR or better) after initial induction and during maintenance therapy is unclear at this time. In the current study, we propose short course daratumumab for newly diagnosed MM patients with very good partial response (VGPR) or better after induction therapy with/without consolidative HDT/ASCT and MRD positive by bone marrow flow cytometry and for patients who were previously MRD negative after induction and consolidation and recently (within last 3 months) turned MRD positive (with no evidence of clinical progression) by bone marrow flow cytometry. All patients must be on standard of care lenalidomide maintenance for at least 6 months at the time of enrollment

All patients will receive a total of 24 weeks of daratumumab therapy (16 mg/kg intravenous infusion weekly for 8 weeks followed by every 2 weeks for 16 weeks) and continue standard of care lenalidomide maintenance therapy. Baseline studies will include bone marrow biopsy and aspirates with the first pulled bone marrow sample sent for multi-parametric flow cytometry as a priority sample to determine MRD status and determine eligibility. Upon completion of protocol therapy or when patients achieve sCR, patients will undergo a repeat bone marrow biopsy and aspirate for MRD assessment and correlative studies.

The study is powered to assess efficacy (as determined by rate of MRD negativity) of daratumumab in combination with standard of care lenalidomide maintenance amongst patients with low burden disease (i.e. MRD positivity). Our study is novel since no prior myeloma study has been designed to target MRD positive disease with the primary endpoint of achieving status MRD negativity. Secondary endpoints include evaluation of sustain MRD negativity, progression-free survival, overall-survival, and comparison of MRD platforms. Based on the rapidly evolving field with new powerful drugs, the anticipation is that MRD will become a new endpoint for future myeloma trials. MSK myeloma service is a global leader in this context.

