9.3 Monitoring

- 9.3.1 Routine labs (CBC, chemistry panel 14, LDH, magnesium, uric acid, phosphate) will be performed every 2 weeks for the first 2 cycles, then on day 1 for cycle 3-6, at end of therapy. Myeloma tests include serum protein electrophoresis, serum immunofixation, beta-2 microglobulin, quantitative immunoglobulins and serum free light chains assay will be performed at baseline, start of each cycle, at end of therapy. Routine labs, and myeloma labs can be performed 24 hrs in advance.
- 9.3.2 Patients will have clinic visits with H&P or standard progress notes assessing for toxicity/side effects at baseline, day 1 of each cycle, end of therapy, 1-month after end of therapy. Treatment window for day 1 of start of each cycle is +/- 7 days. Treatment window for intra-cycle daratumumab doses is +/- 2 days.
- 9.3.3 24-hr urine sample for protein electrophoresis (UPEP) and immunofixation will be performed at baseline
- 9.3.4 At CR/sCR or end of therapy, routine labs (CBC, chemistry panel 14, LDH, magnesium, uric acid, phosphate), myeloma specific tests - serum protein electrophoresis, serum immunofixation, beta-2 microglobulin, quantitative immunoglobulins and serum free light chains assay, lymphocyte subsets, 24-hr urine sample for protein electrophoresis (UPEP) and immunofixation to assess for monoclonal protein in the urine (Bence-Jones proteinuria). A bone marrow aspirate will also be performed to assess the status of minimal residual disease by flow cytometry (Sample sent will be the first bone marrow "pull"). Patient will have clinic visit (relevant clinical laboratories and H&P) 1 month after completing combination therapy to undergo assessment of toxicities/adverse events.

9.3.5 An Echocardiogram (2-D or strain echo) is optional at baseline (Please refer to Section 10.0).

Outside echocardiograms are permissible

9.3.6 Patients will have FDG-PET-CT at baseline, end of therapy or upon suspicion of progressive disease as clinically indicated.

9.3.7 PFS and OS data will be collected for patients.

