- e. Myeloma tests include serum protein electrophoresis, serum immunofixation, 24-hr urine electrophoresis, urine immunofixation, serum free light chains, quantitative immunoglobulins, beta-2 microglobulin and will be performed at baseline.
- f. Bone marrow aspiration and biopsy will be sent for histopathology, flow cytometry, FISH/cytogenetics. Lysate will also be sent for cell sorting into CD 138- and + fractions and whole bone marrow lysate for HOTB storage so molecular profiling with GEP and DNA-based sequencing at baseline can be performed as correlative work.
- g. Bone marrow aspirate and biopsy can be performed +/- 21 days of intended cycle day or achievement of CR/sCR. Bone marrow aspirate and biopsy will be sent to evaluate for histopathology, flow cytometry (bone marrow immunophenotyping of plasma cells), heavy/light chain immunoglobulin rearrangement. Aspirate lysate will also be sent for cell sorting into CD 138- and + fractions and whole bone marrow lysate for HOTB storage so molecular profiling with GEP and DNA-based sequencing at baseline can be performed as correlative work. For patients, reaching CR/sCR MRD negative timepoint earlier where MRD negative status is confirmed at earlier bone marrow evaluation, bone marrow aspiration and biopsy at end of study will be optional. Otherwise, all other bone marrow biopsies are mandatory.
- h. After study therapy ends, follow-up will be 1 month after study end date. Patients may be followed at more frequent time intervals, and thereafter if clinically indicated. Patients who have progressive disease while on therapy will be followed with restaging scans and laboratory tests as clinically indicated. At disease progression, marrow and FDG-PET/CT are optional but recommended.
- i. For patients with initial baseline 24-hr UPEP samples demonstrating ≥ 100 mg/24 hrs, patients will continue to have 24-hr UPEP samples day 1 of each cycle. Once 24-hr UPEP is < 100 mg/24 hrs, patient can have random UPEP with IFE until achieving negativity. If initial baseline 24-hr UPEP sample is IFE positive and/or < 100 mg/24 hrs, patients can have random UPEP samples with IFE until achieving negativity. Once random UPEP and IFE is negative, no further urine samples are needed (unless patient's disease is primarily measurable by 24 hr urines)
- j. FDG-PET scan will be performed on patients at baseline, end of therapy (+/- 21 days) or upon suspicion of progressive disease as clinically indicated.

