 - Not meeting criteria for CR, VGPR, PR or progressive disease. All categories also require no known evidence of progressive or new bone lesions if radiographic studies were performed. Radiographic studies are not required to satisfy these response requirements.
- f) Progressive disease (PD)
 - Requires any one or more of the following:
 - Increase of $\geq 25\%$ of nadir in:
 - Serum M-component and/or (absolute increase must be $\geq 0.5\text{ g/dl}$. The serum M-component increases of $\geq 1\text{gm/dl}$ are sufficient to define relapse if starting M-component is $\geq 5\text{ gm/dl}$.
 - Urine M-component and/or (the absolute increase must be $\geq 200\text{ mg/24h}$
 - Only in patients without measurable serum and urine M-protein levels: the difference between involved and uninvolved FLC levels. The absolute increase must be $>10\text{mg/dl}$.
 - Bone marrow plasma cell percentage: the absolute % must be $\geq 10\%$
 - Definite development of new bone lesions or soft tissue plasmacytomas or definite increase in size of existing bone lesions or soft tissue plasmacytomas
 - Development of that can be attributed solely to the plasma cell proliferative disorder
- g) Relapse from CR
 - Any one or more of the following:
 - Reappearance of serum or urine M-protein by immunofixation or electrophoresis. (Appearance of monoclonal or oligoclonal bands that are different from original isotype may not be defined as "relapse from CR". Often times, such bands may indicate fluctuations in immunological parameters that are not reflective of MM disease. In these situations, immunofixation and electrophoresis will be interpreted by the clinician before being labeled as "relapse"^{23,24}.
 - Development of $\geq 5\%$ plasma cells in the bone marrow
 - Appearance of any other sign of progression (i.e., new plasmacytoma, lytic

bone lesion, hypercalcemia

Progression-Free Survival

PFS is defined as time of start of treatment to time of progression or death, whichever occurs first. Patients alive and progression-free at the end of study will be censored at that time.

Overall Survival

Overall survival is defined as the time of start of treatment to death from any cause. Patients alive at the end of study will be censored at that time.

Toxicity Criteria

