2. Kaplan-Meier methodology will be used to estimate the duration of MRD negativity. This endpoint is defined as the time from MRD negativity achievement to MRD positivity, progression of disease, or death. The median along with the corresponding 95% confidence interval will be estimated.
3. To explore the concordance of different MRD methodologies. MRD status by multiparametric flow cytometry will be compared to next-generation sequencing and to mass spectrometry based proteomics methodologies. The kappa statistic will be reported.
4. Kaplan-Meier methodology will be used to estimate progression-free survival and overall survival. Estimates of survival along with 95% confidence intervals will be provided for select time points.

Exploratory Studies:

1. The gene panel MyType (or alternative equivalent platform) will explore whether any mutations appear to be associated with the achievement of MRD negativity. This analysis is for hypothesis-generation, and all results will be cautiously interpreted. Fisher's exact test may be used to assess any potential association. The variant allele frequency (VAF) will be summarized for each mutation. VAFs will be adjusted for the cancer cell fraction. All results will be adjusted for multiple comparisons.
2. MyType (or alternative equivalent platform) will also be evaluated using samples at the time of progression of disease and will be compared to the pre-treatment baseline samples to explore whether pathways leading to emergence of resistance to the drug regimen can be identified. Similar to the previous objective, this aim is for hypothesis generation, and all results will be cautiously interpreted. Changes in the VAF from baseline will be summarized for patients with an ongoing response and for patients who have progression of disease. A paired t-test may be used to further describe this association. VAFs will be adjusted for the cancer cell fraction.

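### PFS is censored at an undefined end of study, but no disease assessment is scheduled for all patients after about 5.5 months, so later PFS may be biased upward

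*Combined protocol and SAP*

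**What the plan says.** Section 12.1 defines the endpoint: "PFS is defined as time of start of treatment to time of progression or death, whichever occurs first". The censoring rule is: "Patients alive and progression-free at the end of study will be censored at that time". No date or event is given for the end of study. Section 14.1, secondary endpoint 4, adds: "Kaplan-Meier methodology will be used to estimate progression-free survival and overall survival" and "Estimates of survival along with 95% confidence intervals will be provided for select time points". The time points are not named.

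The assessment schedule is as follows.

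- Section 3.2: "All patients will receive a total of 24 weeks of daratumumab therapy".
- Section 9.3.1: the serum myeloma tests "will be performed at baseline, start of each cycle, at end of therapy".
- Section 9.3.6 and Section 10.0 note j: PET-CT at baseline and end of therapy, otherwise on suspicion of progression.
- Section 9.3.4: the visit 1 month after therapy has an examination and relevant laboratory tests, and its stated purpose is toxicity. The Section 10.0 table shows no myeloma tests, marrow or PET-CT at that visit.
- Section 10.0 note h: "After study therapy ends, follow-up will be 1 month after study end date", with anything later only as clinically indicated. The same note says: "At disease progression, marrow and FDG-PET/CT are optional but recommended".
- Section 9.3.7: PFS and OS data are to be collected, with no interval, test or duration.
- Section 14.1, secondary endpoint 1: sustained MRD negativity is judged on a marrow 1 year after treatment. That marrow is not in the Section 10.0 schedule.

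**The concern.** Section 12.1 defines progression by M-protein, free light chains, marrow plasma cells and lesions. Several of these can be seen only if someone tests for them. Section 6.3 excludes patients with measurable disease at entry, so a first sign of progression could be a laboratory rise. PET-CT on suspicion needs something to raise the suspicion, and after end of therapy no test scheduled for all patients does so.

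A patient who is not tested after week 24 but is alive at the end of study is nevertheless carried as progression-free to that date. If progression was missed, or found late, the Kaplan-Meier curve sits too high from about 6 months on. Secondary objective 4 asks for PFS after a short course of treatment, so the later part of the curve is the part of most interest, and it has the weakest ascertainment.

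**Working it through.** **The plan's own figures.** The plan states no PFS figure, so there is none to reproduce. Its only design figures concern MRD negativity (Section 14.1). Continuing with at least 2 of 16 and calling the treatment promising with at least 5 of 25 gives an exact type I error of 0.095 at 10% and power of 0.903 at 30%. This agrees with the plan, and PFS plays no part in it.

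**Inputs**

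- Last disease assessment scheduled for all patients: 24 weeks (Sections 3.2 and 9.3.1). Te = 24 × 7 / 30.4375 = 5.52 months.
- Patients: 25 (Section 14.1).
- Assumption: PFS is exponential with median m of 18, 24, 36 or 48 months.
- Assumption: a share q of the PFS events after Te is found, at the true time. Values used are 0, 50, 75 and 100%.

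**Formula.** True PFS is S(t) = 2^(−t/m). Patients whose progression is not found stay at risk until the end of study, taken here to lie beyond t. Reported PFS is then S(Te) − q × [S(Te) − S(t)].

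**Example, m = 24, t = 12.** S(Te) = 2^(−5.52/24) = 0.853 and S(12) = 2^(−12/24) = 0.707. With q = 50%: 0.853 − 0.5 × (0.853 − 0.707) = 0.780.

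**12-month PFS, %**

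| Assumed median (months) | True | None found | 50% found | 75% found | All found |
|---|---|---|---|---|---|
| 18 | 63.0 | 80.9 | 71.9 | 67.5 | 63.0 |
| 24 | 70.7 | 85.3 | 78.0 | 74.3 | 70.7 |
| 36 | 79.4 | 89.9 | 84.6 | 82.0 | 79.4 |
| 48 | 84.1 | 92.3 | 88.2 | 86.2 | 84.1 |

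If none is found, the overstatement is 17.9, 14.6, 10.5 and 8.2 points. If all is found, it is zero. At 24 months with a 24-month median, the true value is 50.0%, against 85.3, 67.6 and 58.8% with 0, 50 and 75% found.

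**If end of study is the 1-month visit.** The largest overstatement is S(5.52) − S(6.52), which is 3.1, 2.4, 1.7 and 1.3 points for the four medians.

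**What the 1-year marrow could recover.** It falls at 5.52 + 12 = 17.52 months. Between end of therapy and that date, 25 × [S(5.52) − S(17.52)] = 7.5, 6.2, 4.6 and 3.7 patients would have a PFS event. The marrow covers only patients who became MRD negative. Suppose that is 20% (5 of 25, the success threshold) or 30% (the target rate), that they progress at the same rate as the others, and that every progression among them is found at its true time and none elsewhere. With a 24-month median, reported PFS at 17.52 months would be 80.3% or 77.8%, against a true 60.3%.

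**The case against.** The strongest reply is that disease evaluation does not cease at week 24. Clinically indicated follow-up, PET-CT on suspicion, collection of PFS data, research samples at progression at any time, and the 1-year marrow are all in the text. Section 13.1 makes completing treatment a reason to leave therapy, not to leave the study. Section 1.1 also mentions monthly response evaluation without an end date, although Section 9.3.1 ties the tests to cycles. Patients continuing lenalidomide may well have blood tests in routine care. This stands: a reader might infer that testing stops and that PFS is certainly overstated, but the documents support only that later ascertainment is unscheduled and that the curve may be too high.

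Second, end of study may come early. Note h can be read as placing the study end date at end of therapy. On that reading there is no untested time, and at the 1-month visit there is little. This also stands, but PFS would then end at about 5.5 to 6.5 months and say little about what follows a short course. The 1-year marrow, and off-study criteria that do not list completion of treatment, point to a later date. The text does not settle the matter.

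Third, a reader might extend the same bias to duration of MRD negativity, because progression is an event there too. Section 14.1 gives no censoring rule for that endpoint, and the Section 12.1 rule covers only PFS and OS. The gap is an unstated rule, not a demonstrated bias.

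Fourth, the Section 10.0 table was read by machine, and its empty Follow-up column is weak evidence alone. Sections 9.3.1 and 9.3.4 and note h support the point without it.

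**Conclusion.** The point holds as a risk to a secondary endpoint. No disease assessment is scheduled for all patients after about 5.5 months, and PFS is censored at an undefined end of study, not at the last disease assessment. PFS beyond about 6 months therefore rests on unscheduled ascertainment, and missed or late-found progression can only raise the curve.

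Across the assumed medians of 18 to 48 months, the overstatement at 12 months runs from 0 points (everything found) to about 18 (nothing found, 18-month median). It is about 1 to 3 points at most if end of study is the 1-month visit. Both the PFS distribution and the share found are assumptions. The documents give neither, nor any length of observation after treatment from which a definite gap could be computed.

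PFS is descriptive here, with no decision rule attached. The conclusion on MRD negativity is unaffected.

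**What to change.** 1. In Section 12.1, define end of study and censor PFS at the last adequate disease assessment, stating which tests make an assessment adequate.
2. In Section 9.3 and note h of Section 10.0, provide for abstraction of the serum electrophoresis, immunofixation and free-light-chain results already obtained in routine care on lenalidomide maintenance, through at least 1 year after treatment. The documents do not say how often these are done, so the dates should be recorded. If this is not done, limit reported PFS to about 6 months. The first change does not suffice alone: later assessments would come mainly from patients already suspected of progressing, and the few remaining at risk would no longer represent the rest.
3. In Section 14.1, state the censoring rule for duration of MRD negativity, and how PFS treats patients who start other therapy and so leave the study under Section 13.1. Reconcile the 1-year marrow in secondary endpoint 1 with the Section 10.0 schedule and the 1-month follow-up in note h.

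The cost is a few sentences and data-manager time for chart abstraction, with no added procedure. The PFS curve may be shorter or less favourable.

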13.1 CRITERIA FOR REMOVAL FROM STUDY

Off-therapy Criteria

Patients with medically concerning grade 3 or 4 adverse events related to drug therapy may be taken off therapy at the discretion of the principal investigator.

- Hematologic toxicity has not completely resolved or resolved to < grade 1 or baseline after 2 weeks of withholding treatment
- Therapy has been held for more than 3 weeks due to grade 3 or higher non-hematologic toxicity
- Patient completes the protocol treatment
- Progression of disease
- Patient chooses to go off therapy
- The principal investigator may remove patient from protocol therapy if deemed necessary due to medical conditions, compliance, etc.
- Patient becomes pregnant.

Off-Study Criteria

- Patient requests to be withdrawn from study
- Death
- Physician's determination that withdrawal is in the patient's best interest.
- Patient who have gone on to other treatments aside from revlimid

maintenance (5-15 mg daily 21-28/ 28-day cycle)

14.1 BIOSTATISTICS

Study Design/Primary Endpoints

This is a single arm phase II study designed to evaluate the efficacy of short course therapy with daratumumab, in multiple myeloma patients achieving a VGPR or better with MRD positive state while on lenalidomide maintenance for at least 6 months at the time of enrollment. The primary objective of this study is to determine the rate of conversion to MRD negativity by the completion of 6 cycles of treatment.

Rationale

The primary objective of this trial is to determine whether treatment with daratumumab is associated with a substantial fraction of patients with MRD positive multiple myeloma converting to a MRD negative state as assessed by multicolor flow cytometry. Previously studies have reported that approximately 10% of patients will achieve deeper responses including MRD negativity after maintenance therapy with lenalidomide alone¹⁸. The current study will be considered positive if the rate of MRD negativity is 30% or higher with daratumumab.

Power Calculations

This study will implement a Simon's two-stage minimax design to distinguish between an unpromising rate of 10% and a promising rate of 30%. The study is designed to have a type I error and a type II error of 0.10. The maximum sample size is 25 patients.

Primary analysis

In the first stage of the study, a total of 16 patients will accrue. If 2 or more patients achieve MRD negativity, additional 9 patients will accrue. If at the end of the study, 5 patients or more out the total 25 patients achieve MRD negativity, the short course daratumumab will be considered promising for future investigation.

Accrual will be held after the 16th patient if 2 or more patients have not yet achieved MRD negativity. We anticipate that one to two patients will accrue each month.

Analysis population for primary endpoint

All patients who receive at least one dose of daratumumab will be considered evaluable for the primary endpoint. Patients who do not have the end of therapy bone marrow for any reason and have not achieved MRD negativity at any point while on study will be considered a treatment failure.

Secondary endpoints:

1. To estimate the rate of sustained MRD negativity. Among patients achieving MRD negativity, sustained negativity is defined as remaining MRD negative at the 1-year post treatment

completion bone marrow biopsy. The proportion along with the 95% confidence interval will be estimated.

2. Kaplan-Meier methodology will be used to estimate the duration of MRD negativity. This endpoint is defined as the time from MRD negativity achievement to MRD positivity, progression of disease, or death. The median along with the corresponding 95% confidence interval will be estimated.
3. To explore the concordance of different MRD methodologies. MRD status by multiparametric flow cytometry will be compared to next-generation sequencing and to mass spectrometry based proteomics methodologies. The kappa statistic will be reported.
4. Kaplan-Meier methodology will be used to estimate progression-free survival and overall survival. Estimates of survival along with 95% confidence intervals will be provided for select time points.

Exploratory Studies:

1. The gene panel MyType (or alternative equivalent platform) will explore whether any mutations appear to be associated with the achievement of MRD negativity. This analysis is for hypothesis-generation, and all results will be cautiously interpreted. Fisher's exact test may be used to assess any potential association. The variant allele frequency (VAF) will be summarized for each mutation. VAFs will be adjusted for the cancer cell fraction. All results will be adjusted for multiple comparisons.
2. MyType (or alternative equivalent platform) will also be evaluated using samples at the time of progression of disease and will be compared to the pre-treatment baseline samples to explore whether pathways leading to emergence of resistance to the drug regimen can be identified. Similar to the previous objective, this aim is for hypothesis generation, and all results will be cautiously interpreted. Changes in the VAF from baseline will be summarized for patients with an ongoing response and for patients who have progression of disease. A paired t-test may be used to further describe this association. VAFs will be adjusted for the cancer cell fraction.

